#### 4.2.1 Timing of Dose Administration

Trial treatment of doxorubicin, vinblastine, and dacarbazine should be administered on Day 1 and 15 of each cycle after all procedures/assessments have been completed as detailed on the Trial Flow Chart (Section 5.0). Pembrolizumab 200 mg will be administered as a 30 minute IV infusion every 3 weeks starting on cycle 1 day 1. Sites should make every effort to target infusion timing to be as close to 30 minutes as possible. However, given the variability of infusion pumps from site to site, a window of -5 minutes and +10 minutes is permitted (i.e., infusion time is 30 minutes: -5 min/+10 min).

Each cycle of therapy is given every 28 days. Two cycles should be given per protocol. Administration may be +/-2 days. All other infusion details should be as per institutional standard of care.

Pembrolizumab will be administered first, followed by Doxorubicin, Vinblastine and Dacarbazine.

All trial treatments will be administered on an outpatient basis.

Growth factor support will be at the discretion of the treating team. Growth factors should be avoided whenever possible within 10 days of FDG-PET imaging. Antibiotic and antiemetic prophylaxis will be per institutional standard of care.

#### **4.2.2 Dose Modification and toxicity management for immune-related AEs associated with pembrolizumab**

AEs associated with pembrolizumab exposure may represent an immunologic etiology. These immune-related AEs (irAEs) may occur shortly after the first dose or several months after the last dose of pembrolizumab treatment and may affect more than one body system simultaneously. Therefore, early recognition and initiation of treatment is critical to reduce complications. Based on existing clinical study data, most irAEs were reversible and could be managed with interruptions of pembrolizumab, administration of corticosteroids and/or other supportive care. For suspected irAEs, ensure adequate evaluation to confirm etiology or exclude other causes. Additional procedures or tests such as bronchoscopy, endoscopy, skin biopsy may be included as part of the evaluation. Based on the severity of irAEs, withhold or permanently discontinue pembrolizumab and administer corticosteroids. Dose modification and toxicity management guidelines for irAEs associated with pembrolizumab are provided in Table 3.

**Table 3 Dose modification and toxicity management guidelines for immune-related AEs associated with pembrolizumab**

General instructions:				

 
1. Severe and life-threatening irAEs should be treated with IV corticosteroids followed by oral steroids. Other immunosuppressive treatment should begin if the irAEs are not controlled by corticosteroids.
 
2. Study intervention must be permanently discontinued if the irAE does not resolve or the corticosteroid dose is not <math>\leq</math>10 mg/day within 12 weeks of the last study intervention treatment.
 
3. The corticosteroid taper should begin when the irAE is <math>\leq</math> Grade 1 and continue at least 4 weeks.
 
4. If study intervention has been withheld, study intervention may resume after the irAE decreased to <math>\leq</math> Grade 1 after corticosteroid taper.
 
				

irAEs	Toxicity Grade (CTCAE v5.0)	Action With Pembrolizumab	Corticosteroid and/or Other Therapies	Monitoring and Follow-up
Pneumonitis	Grade 2	Withhold	
 
• Administer corticosteroids (initial dose of 1 to 2 mg/kg prednisone or equivalent) followed by taper
 
	
 
• Monitor participants for signs and symptoms of pneumonitis
 

	Recurrent Grade 2, Grade 3 or 4	Permanently discontinue	
 
• Add prophylactic antibiotics for opportunistic infections
 
	
 
• Evaluate participants with suspected pneumonitis with radiographic imaging and initiate corticosteroid treatment
 

Diarrhea/Colitis	Grade 2 or 3	Withhold	
 
• Administer corticosteroids (initial dose of 1 to 2 mg/kg prednisone or equivalent) followed by taper
 
	
 
• Monitor participants for signs and symptoms of enterocolitis (ie, diarrhea, abdominal pain, blood or mucus in stool with or without fever)
 

irAEs	Toxicity Grade (CTCAE v5.0)	Action With Pembrolizumab	Corticosteroid and/or Other Therapies	Monitoring and Follow-up
	Recurrent Grade 3 or Grade 4	Permanently discontinue		
and of bowel perforation (ie, peritoneal signs and ileus)
 
 
Participants with <math>\geq</math>Grade 2 diarrhea suspecting colitis should consider GI consultation and performing endoscopy to rule out colitis
 
Participants with diarrhea/colitis should be advised to drink liberal quantities of clear fluids. If sufficient oral fluid intake is not feasible, fluid and electrolytes should be substituted via IV infusion
 

AST or ALT Elevation or Increased Bilirubin	Grade 2 a	Withhold	
 
Administer corticosteroids (initial dose of 0.5 to 1 mg/kg prednisone or equivalent) followed by taper
 
	
 
Monitor with liver function tests (consider weekly or more frequently until liver enzyme value returned to baseline or is stable)
 

	Grade 3 b or 4 c	Permanently discontinue	
 
Administer corticosteroids (initial dose of 1 to 2 mg/kg prednisone or equivalent) followed by taper
 
	
T1DM or Hyperglycemia	New onset T1DM or Grade 3 or 4 hyperglycemia associated with	Withhold d	
 
Initiate insulin replacement therapy for participants with T1DM
 
	
 
Monitor participants for hyperglycemia or other signs and symptoms of diabetes
 

irAEs	Toxicity Grade (CTCAE v5.0)	Action With Pembrolizumab	Corticosteroid and/or Other Therapies	Monitoring and Follow-up
	evidence of $\beta$ -cell failure		
 
Administer antihyperglycemic in participants with hyperglycemia
 
	
Hypophysitis	Grade 2	Withhold	
 
Administer corticosteroids and initiate hormonal replacements as clinically indicated
 
	
 
Monitor for signs and symptoms of hypophysitis (including hypopituitarism and adrenal insufficiency)
 

	Grade 3 or 4	Withhold or permanently discontinue d		
Hyperthyroidism	Grade 2	Continue	
 
Treat with nonselective beta-blockers (eg, propranolol) or thionamides as appropriate
 
	
 
Monitor for signs and symptoms of thyroid disorders
 

	Grade 3 or 4	Withhold or permanently discontinue d		
Hypothyroidism	Grade 2, 3 or 4	Continue	
 
Initiate thyroid replacement hormones (eg, levothyroxine or liothyronine) per standard of care
 
	
 
Monitor for signs and symptoms of thyroid disorders
 

Nephritis: grading according to increased creatinine or acute kidney injury	Grade 2	Withhold	
 
Administer corticosteroids (prednisone 1 to 2 mg/kg or equivalent) followed by taper
 
	
 
Monitor changes of renal function
 

	Grade 3 or 4	Permanently discontinue		
Neurological	Grade 2	Withhold	
 
Based on severity of AE administer
 
	
 
Ensure adequate evaluation to confirm etiology
 

irAEs	Toxicity Grade (CTCAE v5.0)	Action With Pembrolizumab	Corticosteroid and/or Other Therapies	Monitoring and Follow-up
Toxicities	Grade 3 or 4	Permanently discontinue	corticosteroids	and/or exclude other causes
Myocarditis	Grade 1	Withhold	
 
Based on severity of AE administer corticosteroids
 
	
 
Ensure adequate evaluation to confirm etiology and/or exclude other causes
 

	Grade 2, 3 or 4	Permanently discontinue		
Exfoliative Dermatologic Conditions	Suspected SJS, TEN, or DRESS	Withhold	
 
Based on severity of AE administer corticosteroids
 
	
 
Ensure adequate evaluation to confirm etiology or exclude other causes
 

	Confirmed SJS, TEN, or DRESS	Permanently discontinue		
All Other irAEs	Persistent Grade 2	Withhold	
 
Based on severity of AE administer corticosteroids
 
	
 
Ensure adequate evaluation to confirm etiology or exclude other causes
 

	Grade 3	Withhold or discontinue based on the event c		
	Recurrent Grade 3 or Grade 4	Permanently discontinue		

AE(s)=adverse event(s); ALT= alanine aminotransferase; AST=aspartate aminotransferase; CTCAE=Common Terminology Criteria for Adverse Events; DRESS=Drug Rash with Eosinophilia and Systemic Symptom; GI=gastrointestinal; IO=immuno-oncology; ir=immune related; IV=intravenous; SJS=Stevens-Johnson Syndrome; T1DM=type 1 diabetes mellitus; TEN=Toxic Epidermal Necrolysis; ULN=upper limit of normal.

**Note: Non-irAE will be managed as appropriate, following clinical practice recommendations.**

a AST/ALT: >3.0 to 5.0 x ULN if baseline normal; >3.0 to 5.0 x baseline, if baseline abnormal; bilirubin: >1.5 to 3.0 x ULN if baseline normal; >1.5 to 3.0 x baseline if baseline abnormal

b AST/ALT: >5.0 to 20.0 x ULN, if baseline normal; >5.0 to 20.0 x baseline, if baseline abnormal; bilirubin: >3.0 to 10.0 x ULN if baseline normal; >3.0 to 10.0 x baseline if baseline abnormal

c AST/ALT: >20.0 x ULN, if baseline normal; >20.0 x baseline, if baseline abnormal; bilirubin: >10.0 x ULN if baseline normal; >10.0 x baseline if baseline abnormal

irAEs	Toxicity Grade (CTCAE v5.0)	Action With Pembrolizumab	Corticosteroid and/or Other Therapies	Monitoring and Follow-up
				d The decision to withhold or permanently discontinue pembrolizumab is at the discretion of the investigator or treating physician. If control achieved or $\leq$ Grade 2, pembrolizumab may be resumed.
				e Events that require discontinuation include, but are not limited to: encephalitis and other clinically important irAEs (eg, vasculitis and sclerosing cholangitis).

### **Dose modification and toxicity management of infusion-reactions related to pembrolizumab**

Pembrolizumab may cause severe or life threatening infusion-reactions including severe hypersensitivity or anaphylaxis. Signs and symptoms usually develop during or shortly after drug infusion and generally resolve completely within 24 hours of completion of infusion. Dose modification and toxicity management guidelines on pembrolizumab associated infusion reaction are provided in Table 4.

NCI CTCAE Grade	Treatment	Premedication at Subsequent Dosing
Grade 1 Mild reaction; infusion interruption not indicated; intervention not indicated	Increase monitoring of vital signs as medically indicated until the participant is deemed medically stable in the opinion of the investigator.	None
Grade 2 Requires therapy or infusion interruption but responds promptly to symptomatic treatment (e.g., antihistamines, NSAIDs, narcotics, IV fluids); prophylactic medications indicated for $\leq 24$ hrs	
Stop Infusion.
 
Additional appropriate medical therapy may include but is not limited to:
 
IV fluids
 
Antihistamines
 
NSAIDs
 
Acetaminophen
 
Narcotics
 
Increase monitoring of vital signs as medically indicated until the participant is deemed medically stable in the opinion of the investigator. If symptoms resolve within 1 hour of stopping drug infusion, the infusion may be restarted at 50% of the original infusion rate (e.g. from 100 mL/hr to 50 mL/hr). Otherwise dosing will be held until symptoms resolve and the participant should be premedicated for the next scheduled dose.
 
Participants who develop Grade 2 toxicity despite adequate premedication should be permanently discontinued from further study drug treatment
	
Participant may be premedicated 1.5h (<math>\pm 30</math> minutes) prior to infusion of _____ with:
 
Diphenhydramine 50 mg po (or equivalent dose of antihistamine).
 
Acetaminophen 500-1000 mg po (or equivalent dose of analgesic).

Grades 3 or 4 Grade 3: Prolonged (i.e., not rapidly responsive to symptomatic medication and/or brief interruption of infusion); recurrence of symptoms following initial improvement; hospitalization indicated for other clinical sequelae (e.g., renal impairment, pulmonary infiltrates) Grade 4:	
Stop Infusion.
 
Additional appropriate medical therapy may include but is not limited to:
 
Epinephrine**
 
IV fluids
 
Antihistamines
 
NSAIDs
 
Acetaminophen
 
Narcotics
 
Oxygen
 
Pressors
 
Corticosteroids
 
Increase monitoring of vital signs as medically indicated until the participant is deemed medically stable in the opinion of the investigator.
	No subsequent dosing

Life-threatening; pressor or ventilatory support indicated	
Hospitalization may be indicated.  **In cases of anaphylaxis, epinephrine should be used immediately.  Participant is permanently discontinued from further study drug treatment.
	

Appropriate resuscitation equipment should be available at the bedside and a physician readily available during the period of drug administration.  For further information, please refer to the Common Terminology Criteria for Adverse Events v4.0 (CTCAE)
		

**Table 4 Pembrolizumab Infusion Reaction Dose modification and Treatment Guidelines**

**Other allowed dose interruption for pembrolizumab**

Pembrolizumab may be interrupted for situations other than treatment-related AEs such as medical / surgical events or logistical reasons not related to study therapy. Participants should be placed back on study therapy within 3 weeks of the scheduled interruption, unless otherwise discussed with the Sponsor. The reason for interruption should be documented in the patient's study record.

#### **4.2.3 Randomization or Treatment Allocation**

Patients will not be randomized and will receive APVD.

### **4.3 Stratification**

- The Ann Arbor staging criteria will be utilized;
- The GHSG Risk Stratification will be used for all patients with early stage disease.
- The Hasenclever score will be used for all patients with advanced disease.
- Bulk will be defined as the long axis of the single largest nodal mass.

Concomitant Medications/Vaccinations (allowed & prohibited) Medications used during the course of the study should be documented.

Medications or vaccinations specifically prohibited in the exclusion criteria are not allowed during the ongoing trial. If there is a clinical indication for one of these or other medications or vaccinations specifically prohibited during the trial, discontinuation from trial therapy or vaccination may be required. The final decision on any supportive therapy or vaccination rests with the investigator and/or the participant's primary physician.

#### **4.3.1 Acceptable Concomitant Medications**

All treatments that the investigator considers necessary for a participant's welfare may be administered at the discretion of the investigator in keeping with the community standards of medical care. All concomitant medication will be recorded on the case report form (CRF) including all prescription, over-the-counter (OTC), herbal supplements, and IV medications and fluids. If changes occur during the trial period, documentation of drug dosage, frequency, route, and date may also be included on the CRF.

All concomitant medications received within 28 days before the first dose of trial treatment and 30 days after the last dose of trial treatment should be recorded. Concomitant medications administered after 30 days after the last dose of trial treatment should be recorded for SAEs and ECIs as defined in Section 6.1.2.1.

#### **4.3.2 Prohibited Concomitant Medications**

The administration of concurrent medications intended to treat the primary cancer is not allowed during protocol therapy. This includes any chemotherapy, investigational agent, biologic agent or other anti-tumor agents. Radiation therapy is also prohibited.

Patients should be strongly discouraged from taking any "alternative" or "naturopathic" medications since these agents may interact with APVD.

### 4.3.3 Rescue Medications & Supportive Care

Participants should receive appropriate supportive care measures as deemed necessary by the treating investigator. Suggested supportive care measures for the management of AEs with potential immunologic etiology are outlined along with the dose modification guidelines in Section 4.2.2, [Table 3]. Where appropriate, these guidelines include the use of oral or IV treatment with corticosteroids, as well as additional anti-inflammatory agents if symptoms do not improve with administration of corticosteroids. Note that several courses of steroid tapering may be necessary as symptoms may worsen when the steroid dose is decreased. For each disorder, attempts should be made to rule out other causes such as metastatic disease or bacterial or viral infection, which might require additional supportive care. The treatment guidelines are intended to be applied when the Investigator determines the events to be related to pembrolizumab.

Note: If after the evaluation of the event, it is determined not to be related to pembrolizumab, the Investigator does not need to follow the treatment guidance. Refer to [Table 3] in Section 5.2.2 for guidelines regarding dose modification and supportive care.

It may be necessary to perform conditional procedures such as bronchoscopy, endoscopy, or skin photography as part of evaluation of the event.

When study interventions are administered in combination, attribution of an adverse event to a single component is likely to be difficult. Therefore, while the investigator may attribute a toxicity event to pembrolizumab alone, or to the combination of other chemo drugs, for adverse events listed below, all interventions must be held according to the criteria below.

When study interventions are administered in combination, if the AE is considered immune-related, all interventions should be held according to recommended dose modifications.

Participants may not have any dose modifications (no change in dose or schedule) of pembrolizumab in this study.

- If the toxicity does not resolve or the criteria for resuming treatment are not met, the participant must be discontinued from all study interventions.
- If the toxicities do resolve and conditions are aligned with what is defined below, the combination of study therapies may be restarted at the discretion of the investigator. In these cases where the toxicity is attributed to the other chemotherapy combination or individual drugs, re-initiation of pembrolizumab as a monotherapy may be considered at the investigator's discretion.

### 4.4 Participant Withdrawal/Discontinuation Criteria

Participants may discontinue study treatment at any time for any reason or be dropped from the study treatment at the discretion of the investigator should any untoward effect occur. In addition, a participant may be discontinued from study treatment by the investigator or the Sponsor if study treatment is inappropriate, the trial plan is violated, or for administrative and/or other safety reasons.

Specific details regarding procedures to be performed at study treatment discontinuation are provided in Section 7.1.4 – Other Procedures.

A participant must be discontinued from study treatment but continue to be monitored in the study for any of the following reasons:

- The participant or participant's legally acceptable representative requests to discontinue study treatment
- Confirmed radiographic disease progression outlined in Appendix 3
- Any progression or recurrence of any malignancy, or any occurrence of another malignancy that requires active treatment
- Unacceptable adverse experiences as described in Section 6.2.
- The participant has a medical condition or personal circumstance which, in the opinion of the investigator and/or sponsor, placed the participant at unnecessary risk from continued administration of study treatment.
- The participant has a confirmed positive serum pregnancy test
- Noncompliance with study treatment or procedure requirements
- Recurrent Grade 2 pneumonitis
- Completion of protocol treatment
- The participant is lost to follow-up
- Administrative reasons

#### **4.5 Participant Replacement Strategy**

Subjects who fail to complete study therapy will not be replaced.

#### **4.6 Clinical Criteria for Early Trial Termination**

Early trial termination will be the result of the criteria specified below:

1. Quality or quantity of data recording is inaccurate or incomplete
2. Poor adherence to protocol and regulatory requirements
3. Incidence or severity of adverse drug reaction in this or other studies indicates a potential health hazard to participants
4. Plans to modify or discontinue the development of the study drug

In the event of Merck decision to no longer supply study drug, ample notification will be provided so that appropriate adjustments to participant treatment can be made.

## 5.0 STUDY FLOW CHART – PART A AND PART B

Required Studies	Pre-Entry (within 4 weeks unless indicated otherwise)	Within 2 days prior to each dose 	Post Therapy 	Safety Follow-up Visit 	Follow-up 
Physical					
History and Physical (H&P)	X	X 	X	X	
Performance Status	X	X 	X	X	
Clinical Disease Assessment	X	X 	X		
Adverse Event Assessment	X	X 	X	X	
Lab					
ESR, TSH, T3, T4, LDH	X 		X 	X	
Complete blood count with differential 	X	X 	X	X	
Comprehensive metabolic panel 	X	X 	X	X	
Pregnancy test	X 				
Radiology					
Left Ventricular Ejection Fraction (LVEF)	X 				
PET/CT	X 		X		
Correlative Studies 	X		X		

1. For Cycle 1 Day 1, pre-entry H&P, performance status, disease assessment and adverse event assessment may be used (these do not need to be repeated within 2 days) and labs done within 10 days are acceptable.
2. Pregnancy test in women of childbearing potential.
3. EF must be  $\geq 50\%$  within 56 days.
4. Post therapy (interim PET for patients planning on receiving more than 2 total cycles) studies should be done as early as day 16 of cycle 2 but prior to any additional antineoplastic therapy unless other objective evidence of progressive disease. For patients who proceed with more than 2 cycles of therapy (Optional part A, mandatory 6 cycles for part B), an additional post therapy visit with additional PET/CT should be performed 28-35 days after the expected last dose of chemotherapy, which may also serve as the post treatment safety visit.
5. A safety follow up visit should be performed 28-35 days after last dose of study therapy is administered. This may be an additional visit depending on the date of the post-therapy visit, but may be combined with the post-therapy visit if the windows overlap.
6. Follow-up after cycle 2 will be standard of care. Patient will be tracked for subsequent therapy, response, progression-free, and overall survival after completion of 2 cycles of therapy up to 5 years.
7. Patients must have an ESR, TSH, T3 and T4 performed within 14 days prior to registration.
8. Dose is defined as a day in which one receives any of the medications outlined in section 4.2
9. See Table 6 for list of components
10. LDH and ESR not required at Post Therapy or Safety follow up visit
11. PET/CT may be performed within 42 days.
12. Correlative studies may be carried out whenever possible and include PD1/PLDL1/PDL2 expression, MRD (e.g. Adaptive Clonoseq or similar) and cytokine monitoring. This may include up to 10 unstained slides of diagnostic tissue or tissue block as well as up to 20 cc of whole blood and serum at the following (but not limited to) timepoints: baseline, cycle 2 day 1, cycle 3 day 1, and end of treatment.

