## 2.0 TRIAL DESIGN

### 2.1 Trial Design

This is a nonrandomized, single-arm pilot study designed to evaluate Adriamycin, Pembrolizumab, Vinblastine, and Dacarbazine for 2 cycles (28 day cycle length) in patients with untreated Classical Hodgkin Lymphoma. Patients can receive an additional 4 cycles, up to a total of 6 cycles of APVD at the discretion of the treating provider (Part A only). All subjects should receive 6 total cycles in Part B.

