### **6.2 Assessing and Recording Adverse Events**

Routine reporting is required for all grade 3, 4 and 5 adverse events. Grade 1 or 2 AEs will not be captured or reported with the exception of ANC, platelet nadirs, or immune related adverse events. Routine reports include data after each cycle of therapy and 30 days after the last dose of study drugs, or until the patient receives an alternative anti-cancer therapy, whichever date comes first.

Routine reporting will be conducted in accordance with FHCRC/Cancer Consortium IRB policies, applicable FDA regulations, and agreements with Merck.

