#### **6.3.1.1.1 Evaluating Adverse Events**

Table 7 Evaluating Adverse Events

An investigator who is a qualified physician, will evaluate all adverse events as to:

V4.0 CTCAE Grading	Grade 1	Mild; asymptomatic or mild symptoms; clinical or diagnostic observations only; intervention not indicated.
	Grade 2	Moderate; minimal, local or noninvasive intervention indicated; limiting age-appropriate instrumental ADL.
	Grade 3	Severe or medically significant but not immediately life-threatening; hospitalization or prolongation of hospitalization indicated; disabling; limiting self-care ADL.
	Grade 4	Life threatening consequences; urgent intervention indicated.
	Grade 5	Death related to AE
Seriousness	A serious adverse event is any adverse event occurring at any dose or during any use of Merck product that:	
	† Results in death; or	
	† Is life threatening; or places the participant, in the view of the investigator, at immediate risk of death from the event as it occurred (Note: This does not include an adverse event that, had it occurred in a more severe form, might have caused death.); or	
	† Results in a persistent or significant disability/incapacity (substantial disruption of one's ability to conduct normal life functions); or	
	† Results in or prolongs an existing inpatient hospitalization (hospitalization is defined as an inpatient admission, regardless of length of stay, even if the hospitalization is a precautionary measure for continued observation. (Note: Hospitalization for an elective procedure to treat a pre-existing condition that has not worsened is not a serious adverse event. A pre-existing condition is a clinical condition that is diagnosed prior to the use of a Merck product and is documented in the patient's medical history.); or	
	† Is a congenital anomaly/birth defect (in offspring of participant taking the product regardless of time to diagnosis); or	
	Is a new cancer (that is not a condition of the study) (although not serious per ICH definition, is reportable to the Sponsor within 24 hours and to Merck within 2 working days to meet certain local requirements); or	

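### No thyroid test is scheduled in cycles 3–6, so a six-cycle patient has an 18–21 week gap between panels that holds 5 of the 8 pembrolizumab doses

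*Combined protocol and SAP*

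**What the plan says.** The Section 5.0 flow chart is headed as applying to both parts. Its thyroid row, "ESR, TSH, T3, T4, LDH", is marked at pre-entry, post therapy and safety follow-up. The column for tests within two days before each dose is blank for that row, although blood count and metabolic panel are marked there. Footnote 10 waives only LDH and ESR at the later visits, so TSH, T3 and T4 remain due.

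Footnote 4 places the first post-therapy studies from day 16 of cycle 2 until further treatment starts. For patients who go beyond two cycles, "an additional post therapy visit with additional PET/CT should be performed 28-35 days after the expected last dose of chemotherapy". Footnote 5 puts the safety visit 28–35 days after the last dose of study therapy. Section 2.1 makes the long course standard in Part B: "All subjects should receive 6 total cycles in Part B".

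On thyroid toxicity, Table 3 sets pembrolizumab actions by grade for hyperthyroidism and hypothyroidism. It directs thyroid hormone replacement for hypothyroidism of grades 2–4, and gives the monitoring instruction "Monitor for signs and symptoms of thyroid disorders". The text of Section 4.2.2 that introduces Table 3 calls early recognition of immune-related events critical. Section 6.2 states: "Grade 1 or 2 AEs will not be captured or reported with the exception of ANC, platelet nadirs, or immune related adverse events". Section 6.1 allows procedures at unscheduled times when the investigator judges them clinically necessary.

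**The concern.** For a two-cycle patient the schedule covers all three pembrolizumab doses: a panel before the first and another after the third. For a six-cycle patient the same row leaves cycles 3–6 without a scheduled panel, and most of the pembrolizumab is given then.

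Section 6.2 asks for immune-related events of any grade. Table 7 describes grade 1 as "Mild; asymptomatic or mild symptoms; clinical or diagnostic observations only; intervention not indicated". Part of that category has no symptoms, so history and examination before each dose cannot be relied on to reveal it. Thyroid function differs here from liver enzymes and glucose, which also underlie Table 3 events but are measured before every dose in the metabolic panel.

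What is at stake is safety ascertainment. An asymptomatic abnormality arising in cycles 3–6 may first be seen after the last dose, possibly months after it began. Hormone replacement, where Table 3 would call for it, could then be delayed. An abnormality that came and went between the two panels could go unrecorded.

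**Working it through.** The documents state no figure for the interval between thyroid tests, so it is derived from the calendar.

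**Inputs**
- Cycle length: "Each cycle of therapy is given every 28 days" (Section 4.2.1).
- Pembrolizumab interval: "Pembrolizumab 200 mg will be administered as a 30 minute IV infusion every 3 weeks starting on cycle 1 day 1" (Section 4.2.1).
- Pembrolizumab days in the Part B table (Section 2.2): C1D1, C1D22, C2D15, C3D8, C4D1, C4D22, C5D15, C6D8.
- Last chemotherapy: C6D15 (same table).
- Visit windows: Section 5.0, footnotes 4 and 5.

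**Step 1. Study days.** Study day = (cycle − 1) × 28 + cycle day. Pembrolizumab falls on days 1, 22, 43, 64, 85, 106, 127 and 148. All seven intervals are 21 days, which reproduces the stated three-weekly schedule and confirms the conversion.

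**Step 2. Panel after cycle 2.** Earliest: C2D16 = 28 + 16 = day 44. Latest: just before C3D1 = 56 + 1 = day 57.

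**Step 3. End-of-treatment panel.** C6D15 = 5 × 28 + 15 = day 155. Window: 155 + 28 = day 183 to 155 + 35 = day 190. Day 155 is also the last day of any study drug, so the safety visit has the same window and adds no earlier panel.

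**Step 4. Gap**

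| | Calculation | Days | Weeks |
|---|---|---|---|
| Shortest | 183 − 57 | 126 | 18.0 |
| Longest | 190 − 44 | 146 | 20.9 |

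Allowing the ±2-day administration window at both ends gives (155 − 2 + 28) − (57 + 2) = 122 days (17.4 weeks) to (155 + 2 + 35) − (44 − 2) = 150 days (21.4 weeks).

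**Step 5. Doses inside the gap.** Days 64, 85, 106, 127 and 148 lie between the two panels for every permitted combination of visit dates: 5 of 8. The other three (days 1, 22 and 43) precede the first post-baseline panel. The end panel comes 183 − 148 = 35 to 190 − 148 = 42 days after the last pembrolizumab dose.

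**Step 6. Draws already scheduled in cycles 3–6.** Study drug is given on days 57, 64, 71, 85, 99, 106, 113, 127, 141, 148 and 155. That is 11 dosing days, each with a blood count and metabolic panel beforehand.

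**The case against.** The strongest reply is that nothing in the protocol is strictly contradicted. Table 3 asks for monitoring of signs and symptoms, and the flow chart supplies history, examination and adverse-event assessment before every dose. Section 6.2 requires immune-related events to be captured, not screened for in the laboratory. No section sets a required thyroid-test interval or gives a thyroid event rate, so the documents offer no benchmark by which 18–21 weeks is too long. All of this stands. The point is that the schedule fits the protocol's own aims poorly, not that a stated interval is broken.

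A reader might infer more than the documents support:

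- **That no thyroid test can occur in cycles 3–6.** Section 6.1 allows unscheduled testing, and Section 4.2.2 asks for adequate evaluation of suspected events. Both depend on suspicion, so they do little for events without symptoms.
- **That dosing decisions are generally lost.** Table 3 continues pembrolizumab for hypothyroidism of grades 2–4 and for grade 2 hyperthyroidism. Only grade 3–4 hyperthyroidism changes thyroid-related dosing, and Table 7 describes those grades as severe or life-threatening, so they are less likely to be silent.
- **That grade 1 events cannot be found clinically.** Table 7 also includes mild symptoms and clinical observations in grade 1. Only the asymptomatic part depends on a test.
- **That Part B event rates will be wrong.** Section 7.1 plans no analysis of immune-event rates or onset times, and an event persisting to the end panel is still counted.
- **That the row was carried over by oversight from a two-cycle design.** Footnote 6 still speaks of follow-up after cycle 2, while Section 6.1.4.6 was updated for Part B, and Section 1.0 still gives an average treatment length of 2 months. These are suggestive, but footnote 4 was extended to six cycles, and a deliberate choice is also possible. No reason is given either way.

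**Conclusion.** The point holds as a gap in scheduled safety ascertainment. A six-cycle patient goes 126–146 days (18–21 weeks) between scheduled thyroid panels, with 5 of 8 pembrolizumab doses in that interval. If the panel after cycle 2 is normal and the end panel is not, the onset of an asymptomatic event is known only to within that span. How many events would be late or missed cannot be estimated, because the documents give no thyroid event rate.

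The planned 20 Part B patients are all affected, as are Part A patients who take all optional cycles; the documents do not say how many these are. The Part A primary endpoint (dose delay over two cycles), the PET result after cycle 2 and 1-year EFS are untouched. The point rests on thyroid events alone. Hypophysitis is left out because the documents do not name thyroid tests as the means of detecting it.

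The figures assume that treatment runs to schedule, that visits fall within their windows, and that a blank flow-chart cell means no test is scheduled. A delay that pushes back the last chemotherapy and its follow-up visit would lengthen the gap. The change is worth making because it is cheap and serves aims that the protocol itself states.

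**What to change.** Reconcile the Section 5.0 flow chart with Section 4.2.2, Table 3 and Section 6.2. For every patient continuing beyond cycle 2, mark the thyroid tests already listed in Table 6 at one or more of the existing pre-dose blood draws in cycles 3–6, at timepoints the sponsor chooses, with a footnote saying so. No dose, stopping or treatment rule needs to change, and action on results stays as Table 3 has it. If leaving these cycles without a scheduled panel was intended, the protocol should say so and give the reason.

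The cost is a flow-chart amendment and the added assays. Blood is already drawn before each dose, so no extra visit is needed. The drawback is that more low-grade thyroid findings will have to be recorded.
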